7.2.1.1 Collection and Handling of PK Specimen(s)

Blood samples for pharmacokinetic analysis will be processed in the following manner:

- Completely fill a 2-mL lavender-top, K₂EDTA blood collection tube. Mix immediately by gently inverting the tube at least 8 to 10 times to ensure thorough mixing of the anticoagulant.
- Document the actual time and date of collection on the PK Collection Form (Appendix E).
- Immediately after collection, place the blood sample on ice, in a refrigerator (2°C to 8°C), or in an equivalent cooling device until centrifugation for preparation of plasma. Within 30 minutes of blood collection, centrifuge the blood samples in a refrigerated centrifuge (~4°C) at approximately 2000 x g for 10 minutes.
- Use a new polyethylene disposable pipette to divide the plasma into two pre-labeled screw-cap 2 mL polypropylene cryovial plasma storage tubes (i.e., Primary PK Sample and Backup PK Sample). Ensure equal amounts (approximately 0.5 mL) are transferred to each aliquot tube. If the supernatant is limited (approximately 0.5 mL or lower), it should be transferred entirely to the Primary PK sample tube.
- **Immediately place the PK Samples upright in a sample storage cryobox and transfer them to a -80°C or a -20°C freezer.**

The plasma samples will be labeled with patient's initial and ID number, UC protocol number, initials of phlebotomist, sample ID (i.e. Day 29, Day 50, etc) and date of blood collection. Actual blood sampling times will be noted for each patient in the attached flow sheet (pharmacology referral form, appendix E). Any delays or problems will be carefully noted under comments along with the initials of the phlebotomist.

PK samples obtained of the UC will be transported to the BioFluids Core Facility (Room AB201, Scientific Director, [name]) to be stored at -80°C. For all PK sampling, the time of blood collection will be recorded on the specimen collection sheet as well as tube label by the phlebotomist.

PK samples from participating institutions other than the University of Chicago will be collected and processed according to the same methods and stored at the participating

institutions at -80°C (or -20°C if -80°C not available, provided it is not a “self-defrosting” model due to variability in temperature for these models) for shipment. Cryotubes for plasma storage will be provided by the University of Chicago as will blank labels. Frozen PK samples will be shipped to [name] in a styrofoam container (not supplied by UC). Samples will be batched and shipped together with each dose level cohort (Phase I) or quarterly (for phase II).

7.3 Off Study Assessments

Patients will be followed with these assessments until taken off study. Upon study discontinuation, subjects will undergo a complete evaluation with a history and physical examination, ECOG performance status, concomitant medications, and toxicity documented at this visit. The subject will also have standard laboratory studies collected at this visit (CBC, serum chemistries, LDH, PSA, testosterone), and have radiologic tumor assessments performed, unless already performed within four weeks of being taken off study. Study participant refusal or inability to undergo these evaluations should be noted. This visit should be done on the day patients are taken off study medication but may be completed within 30 days of coming off treatment. A third CTC sample will be obtained. In addition, a second optional pre-study tumor biopsy will be obtained at time of disease progression for those coming off study for progression.

[Rest of Page Intentionally Left Blank for Formatting Purposes]

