13.0 STATISTICAL CONSIDERATIONS

13.1 Sample Size/Primary Endpoint

Within the phase I portion of the study, steady-state C_{trough} for Enzalutamide and the active metabolite will be determined for each patient and means and standard deviations calculated. As described above, the mean of the ratio of C_{trough} for Enzalutamide and the active metabolite will be calculated for each dosing cohort, and mean value will be used for dos adjustment determinations. Standard deviation and range of the C_{trough} and ratio will also be calculated and reported.

The randomized phase II study, will be conducted with appropriate sample size to power primary endpoint- to determine if mifepristone in combination with enzalutamide prolongs time to PSA progression compared to enzalutamide alone in patients with metastatic castration resistant prostate cancer. The primary statistical consideration will be PSA progression-free survival (PFS) post randomization, defined as the time to PSA progression or death, whichever comes first. PSA progression will be defined as a PSA (confirmed 2 weeks later) that is ≥ 1.25 times (25% increase) the PSA at randomization (week 12). We assume the median time to PSA progression in the control (enzalutamide alone) arm will be 6 months post randomization. The rationale for this assumption is as follows. In the phase III enzalutamide (AFFIRM) trial¹³, ~10% of treated patients had PSA progression prior to 12 weeks. The PSA progression-free rate was ~42% at 9 months, which would correspond to a 6-month rate, conditional on no event at 12 weeks, of $0.42/0.9=0.47$. Thus our enrichment strategy should lead to a patient population with a median PFS of 6 months (24 weeks) in the control arm post randomization. In order to detect a hazard ratio (HR) of 0.60, which corresponds to an increase in the median from 24 to 40 weeks, with 80% power, a sample

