size of 84 patients (42/arm) is required, using a one-sided test at the $\alpha=0.10$ significance level. This assumes a two-year accrual period and a subsequent one-year follow-up period. Kaplan-Meier⁴¹ curves will be generated and the two treatment arms compared using a logrank test. Median time to event in each group will be estimated along with 90% confidence intervals using the method of Brookmeyer and Crowley⁴². Cox⁴³ proportional hazards regression models will be fit to assess and adjust for the effects of baseline covariates. Overall survival and radiographic progression-free survival will be analyzed similarly. The relative PSA change within each arm will also be reported using a waterfall plot according to working group recommendations for phase II studies in CRPC, as a secondary endpoint⁴⁴. Adverse events will be summarized by grade and type and compared between groups using chi-square or Fisher's exact tests.

For the secondary endocrine PD endpoint, we will compare endocrine PD marker differences between the enzalutamide alone versus the Enzalutamide + Mif treatment arms. In previous placebo controlled trials of Mif, serum cortisol levels reliably doubled from a baseline of approximately 15 $\mu\text{g}/\text{dL}$ to $>30 \mu\text{g}/\text{dL}$ after treatment with mifepristone^{38,39}. Based on the reported interquartile ranges, and assuming normality of the distribution, the coefficient of variation is estimated at 50%. An interim futility analysis will be conducted after half (35) of the expected 70 PSA events are observed. At this stage we will conduct an interim analysis of the difference in cortisol levels; a lack of biomarker effect would provide justification for closing the trial. Thus, assuming a true mean for the control arm of 15 and standard deviation of 7.5 on day 29 post randomization, our sample size will provide 90% power to detect a difference of 15 vs. 22 $\mu\text{g}/\text{dL}$ between the two treatment arms, based on t-test at a two-sided alpha level of 0.05. This calculation allows for a 15% missing data rate prior to day 29 post randomization. The other endocrine laboratories collected at day 29, will be similarly compared between treatment groups.

In addition, if at the interim analysis the conditional power for the primary PSA endpoint is $<25\%$, we will consider terminating the trial for futility. This stopping rule will provide minimal power loss ($<3\%$)⁴⁴.

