13.3 Analysis of Secondary Endpoints

The stratified log-rank will be used to compare the two treatment arms with respect to progression-free survival (PFS). PFS is defined above. For patients without disease progression at the time of analysis, PFS will be censored at the time of the patient's last tumor assessment. The Kaplan-Meier approach will be used to estimate PFS distribution and the proportional hazards model will be used to assess the importance of treatment arm in predicting PFS.

The pharmacokinetic data will be obtained from PK samples described above (Section 7.2.1.). These PK parameters will be summarized using standard descriptive methods (means, standard deviations, medians and ranges).

The primary objective of the exploratory CTC aim is to assess intra- and inter-patient variability in AR and GR expression within CTCs from patients with progressive CRPC. The second objective of this aim is to explore the correlation between baseline AR and GR expression and PSA progression-free survival in patients treated with enzalutamide ± mifepristone. The median/range, mean/standard deviation of expression (relative fluorescence) for AR and GR will be summarized for each patient (intra-patient variability) and for the entire population (inter-patient variability). The components of variability will be estimated using analysis of variance. In addition percent nuclear/cytoplasmic/both cellular localization will be calculated for both receptors. Finally, Cox regression models for time to PSA progression will be fit using the expression of AR and GR as covariates incorporating treatment-by-marker interaction terms to determine whether they have prognostic and/or predictive value. Based on prior studies in this patient population ~50-60% of patients enrolled will have CTCs isolated and available for imaging. The percentage of patients with CTC's following 12 weeks of enzalutamide is unknown, but likely lower, and thus we will assume 30% will have evaluable CTC's at the time of randomization. This should provide ~25 patients (.3x82) for analyses.

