Appendix C

PROSTATE-SPECIFIC ANTIGEN WORKING GROUP CRITERIA⁴⁹

Progressive Disease after Androgen Deprivation Eligibility Criteria:

PSA evidence for progressive prostate cancer consists of a PSA level of at least 5 ng/ml which has risen on at least 2 successive occasions, at least 2 weeks apart. If the confirmatory PSA (#3 below) value is less (i.e., #3b) than the screening PSA (#2) value, then an additional test for rising PSA (#4) will be required to document progression.

Procedures for Assessing PSA Progression Post Study Treatment

PSA measurements will be taken on a monthly basis. PSA increases and decreases will be tracked in order to assess disease response.

PSA partial response is defined by at least a 50% decline from screening (baseline) PSA value. The decline must be confirmed by a second PSA value obtained 4 or more weeks later.

PSA progressive disease may be defined in both patients who have not shown a decrease in their PSA and those who have. For patients who have not shown a decrease, progressive disease is defined as an increase of 25% over the screening (baseline) PSA value and an increase in the absolute-value PSA level by at least 5ng/mL. This increase should be confirmed by a second value.

For those patients whose PSA have decreased but has not reached response criteria, progressive disease is defined as 25% increase over the nadir PSA value provided that the increase is at least 5ng/mL and is confirmed.

Duration of PSA Response

Duration of PSA Response is measured from the time when the PSA value first declines by at least 50% of the screening (baseline) and that was eventually confirmed by a second value. It is calculated until the time at which there is an increase of 50% of PSA nadir, provided the absolute increase is at least 5 ng/mL. The increase must be confirmed by a second consecutive measurement that is at least 50% above the nadir.

If the PSA never shows a 50% increase over the nadir value, then the patient will be censored at the last PSA measurement.

Time to Disease Progression

For patients who have achieved a $\geq 50\%$ decrease from the screening (baseline) PSA, assessment of time to disease progression is when the PSA has increased 50% above the nadir and at a minimum of 5ng/mL. For patients without a PSA decrease of this magnitude or without a decrease, the time for progression is calculated at the time a 25% increase from screening (baseline) PSA has been achieved.

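### Efficacy data collection ends at one off-study visit, although the primary endpoint counts deaths, overall survival is to be analysed, and patients can stop drug before the primary PSA event

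*Combined protocol and SAP*

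**What the plan says.** **Follow-up.** Section 7.3: "Patients will be followed with these assessments until taken off study". The off-study visit falls on the day drug stops or up to 30 days later. The Section 8 calendar ends with that visit, and Section 7.2 schedules imaging only for patients on study.

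**Analysis.** Section 13.1 sets the primary endpoint as PSA progression-free survival, "defined as the time to PSA progression or death, whichever comes first". PSA progression is a confirmed value at least 1.25 times that at randomisation ("25% increase) the PSA at randomization (week 12"). On timing: "This assumes a two-year accrual period and a subsequent one-year follow-up period". On further endpoints: "Overall survival and radiographic progression-free survival will be analyzed similarly".

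**Stopping.** Section 6 ends therapy for progression under Appendices C and D, toxicity, withdrawal of consent or investigator decision. Section 9.3 ends participation after a toxicity hold beyond 28 days. Section 9.10 requires study treatment to stop if other systemic anticancer therapy is needed. Under Appendix C, after a PSA fall of at least 50% from screening, "assessment of time to disease progression is when the PSA has increased 50% above the nadir and at a minimum of 5ng/mL".

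**Censoring.** Section 13.1 gives no rule for the primary endpoint. Section 13.3, on secondary endpoints, has "For patients without disease progression at the time of analysis, PFS will be censored at the time of the" last tumor assessment. Appendix C, on duration of PSA response, has "then the patient will be censored at the last PSA measurement".

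**The concern.** The analysis needs data that the schedule does not collect. A patient who stops drug without the primary event has no further PSA, scan or vital-status check planned for efficacy. The log-rank test can use him only up to his last PSA, so he is in effect censored there whether or not a rule says so. Because death is part of the primary endpoint, a later death is lost to that endpoint as well as to overall survival.

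This matters for two reasons. Lost events cost power. Also, the trial is open label and only one arm adds mifepristone, so exits for toxicity or by investigator decision need not be balanced or unrelated to prognosis. If they are neither, the comparison depends partly on who left and why, and the bias can go in either direction.

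**Working it through.** **1. Contact after drug stops.** I looked for any later contact that would fill the gap.
- Section 10.1 records adverse events to 30 days. Section 10.8.3 follows certain ongoing or possibly related events beyond that. Both are safety follow-up and do not collect later unrelated deaths.
- Section 11.1 uses unscheduled PSA values but asks for none after exit.
- Appendix D asks for an effort to document progression after symptomatic deterioration, without a schedule, PSA or vital status.
- Appendix C mentions monthly PSA under a heading containing the words *Post Study Treatment*. If that means after treatment ends, it contradicts Section 7.3 and the calendar.

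**2. PSA stopping definition against primary event.** These are assumed values in ng/mL, with screening and randomisation PSA equal. Appendix C is applied for a fall of 50% or more, with its 5 ng/mL minimum read as a required rise. Section 6 does not assess PSA progression before the first 12-week visit.

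| PSA at randomisation | Nadir | Appendix C: larger of 1.5 × nadir and nadir + 5 | Primary event: 1.25 × randomisation |
|---|---|---|---|
| 40 | 20 | 30 | 50 |
| 40 | 10 | 15 | 50 |
| 8 | 4 | 9 | 10 |
| 6 | 3 | 8 | 7.5 |

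In the first row the gap is log2(50/30) = 0.74 doublings. In the second it is log2(50/15) = 1.74 doublings. At PSA 8 the gap nearly closes, and at PSA 6 the order reverses. For falls below 50%, Appendix C gives two rules, 25% over nadir or 25% over screening. With PSA 40 and nadir 24 they give 30 or 50, so the gap depends on which applies.

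**3. The plan's own figures.** Inputs from Section 13.1: hazard ratio 0.60, one-sided alpha 0.10, power 80%, 24 months' accrual, 12 months' follow-up, 42 per arm.
- Events needed = 4(1.2816 + 0.8416)² / ln(0.6)² = 69.1; the plan expects 70.
- With exponential times, P(event) = 1 − [exp(−12λ) − exp(−36λ)] / (24λ), λ = ln 2 / median. Medians of 6 and 10 months give 0.915 and 0.788, so 42 × (0.915 + 0.788) = 71.5 events. Medians of 24 and 40 weeks give 0.930 and 0.813, so 73.2 events.
- Power = Φ(√E/2 × 0.5108 − 1.2816) = 81.0% and 81.7%.

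The figures reproduce with no loss. The only missing-data allowance in Section 13.1 is for the day-29 cortisol comparison.

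**4. Random loss of events (assumed rates).**

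| Loss | Events | Power |
|---|---|---|
| 10% | 64.4-65.9 | 78-79% |
| 15% | 60.8-62.2 | 76-77% |
| 20% | 57.2-58.6 | 74-75% |

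**5. Informative exits (assumed rates and hazards).** Log-rank simulations under no treatment effect used 20,000 trials, 42 per arm and a 24-week median. Leavers come from a higher-hazard group equally frequent in both arms and are censored at exit. Nominal one-sided error is 10%.

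| Exits, combination vs control | Weeks | Leavers' hazard | Type I error |
|---|---|---|---|
| 20% vs 5% | 0-12 | 1.5-3 × | 13-17% |
| 5% vs 20% | 0-12 | 1.5-3 × | 5.5-8% |
| 20% vs 5% | 12-36 | 1.5-3 × | about 12% |
| 10% vs 5% | 0-12 | 1.5-3 × | 11-12% |
| 15% vs 15% | 0-12 | 1.5-3 × | about 10% |
| 20% vs 5% | 0-12 | 1 × (not prognostic) | about 10% |

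**6. Overall survival, illustration only.** Assume exit at the Section 13.1 event plus 30 days, deaths independent of PSA progression, and median survival of 18 months. Then 10.7 of 24.7 control deaths (43%) and 13.9 of 24.8 combination deaths (56%) per 42 patients would be seen in the design period.

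**The case against.** - **Choice of analysis.** Following patients only while on drug could be defended as the question of interest. PSA after exit may reflect other therapy, which Section 9.10 makes foreseeable. This stands in part. In the 20% versus 5% scenario (weeks 0-12), continued PSA follow-up restores about 10% error only if later therapy leaves PSA unchanged. If it multiplies the event hazard by 0.75 or 0.5, error is 11-13% or 14-19%. Neither analysis is free of bias, but without later data only one of them can be done.
- **Censoring is implied.** Both written rules censor at the last assessment, and a Kaplan-Meier analysis would do the same. That is fair: the missing rule alone is closer to missing detail. The missing data are the larger gap.
- **The PSA mismatch.** A reader might infer that it inflates type I error because more combination patients would leave on the nadir rule. The documents do not support that. If mifepristone has no effect on PSA, the shares leaving this way are equal on average and error stays near 10%; what remains is lost power. The gap is not universal either. Low PSA can shrink or reverse it, and at a one-month doubling time a gap of 0.74 doublings is about 3.2 weeks, inside the 30-day visit window.
- **Survival capture.** A reader might take the 43% and 56% as estimates. They rest on an outside survival median, on independence, and on exit at the Section 13.1 event and not the Appendix C event. They show only that many deaths could be missed.
- **Toxicity exits.** Section 9.3 advises adjusting mifepristone first, and calendar footnote j ties the last visit to the last enzalutamide dose. Whether stopping mifepristone alone ends assessments is therefore unclear, and early exits may be fewer than assumed.
- **Figures not visible.** The trial schema and phase II timeline could not be read in full; the absence of later follow-up is judged from the text and calendar.

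**Conclusion.** The concern holds on the text and does not depend on any assumed rate. No efficacy data are scheduled after the off-study visit, while the primary endpoint includes death, a year of further follow-up is assumed and overall survival is to be analysed. Patients can stop drug before the primary event, including on a PSA definition that differs from the primary one.

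The size does depend on assumptions, because the documents give no exit rates. A 10-20% event loss lowers power from 81-82% to about 79-74%. Type I error moves away from 10% only when exits are both unequal and prognostic: about 13-17% at 20% versus 5% early exits, 5.5-8% if reversed, and 11-12% at 10% versus 5%. It would go too far to conclude that the primary comparison will be biased, or biased in favour of the combination. The sample size itself is correct on its stated inputs. Overall survival is not a listed objective, so its loss matters less than the effect on the primary endpoint. The plan should be changed because the change is cheap and unrecorded data may not be recoverable later.

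**What to change.** 1. **Section 7.3 and calendar.** For randomised patients who stop study drug without the primary event and have not withdrawn consent, record routine PSA until that event and the start date of any new anticancer therapy. For all randomised patients, record vital status by chart or telephone every 3 months. Continue both to the end of the one-year follow-up in Section 13.1. Say what *Post Study Treatment* means in Appendix C and whether stopping mifepristone alone ends assessments.
2. **Section 13.1.** Analyse PSA progression-free survival in all patients as randomised, censoring those without an event at the last PSA and not at drug discontinuation. Add a sensitivity analysis censoring at the start of new anticancer therapy. State that later therapy can change PSA, so neither analysis is free of bias.
3. **PSA definitions.** Reconcile Section 6, Section 13.1 and Appendix C, including the two rules within Appendix C for smaller falls. Which clinical stopping rule applies is for the sponsor to decide.
4. **Overall survival.** If survival will not be collected, delete the analysis.

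The cost is amendment wording and a little chart abstraction, with no extra visits or patients. The drawback is that some later PSA values will reflect other therapy, which is why the sensitivity analysis and its caveat are needed.

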8.0 STUDY CALENDAR

	Screening ^m	Day1, 15, 29, 43, 57 then Monthly ^g	Every 3Months ^g (beginning at start of concomitant dosing)	Offstudy visit ^j
Procedures				
Informed Consent ^a	X			
Medical History, including demographics	X			
Physical exam, including height (only at screening) and weight	X	X	X	X
Vital Signs ^b	X	X	X	X
ECOG performance status	X	X	X	X
Concomitant medications	X	X	X	X
Adverse Events		X	X	X
EKG	X	X ⁱ		
Laboratory Assessments				
CBC with platelets & Differential counts	X	X	X	X
Serum chemistry and electrolytes ^c	X	X	X	X
LDH	X	X	X	X
PSA	X	X	X	X
Testosterone	X		X	X
Hypothalamic-pituitary labs		X ^k		
PK sample-per Sec. 7.2.1		X ^h		
TumorAssessments^d				
Bonescan/F18 PET ^e	X		X	X
CT or MRI of the abdomen/pelvis	X		X	X
CT chest ^f	X		X	X
Correlative Studies				
Circulating tumor cell (CTC) collection	X	X ⁱ		X
Tumor biopsies (optional)	X			X

- a. Written informed consent must be obtained before any study-specific screening assessments are performed (it can be no more than 28 days prior to starting/beginning study medication).
- b. Includes blood pressure, pulse, respiratory rate, and body temperature.
- c. Serum chemistry includes BUN, creatinine, ALT, AST, glucose, alkaline phosphatase, total bilirubin, electrolytes (K+, Cl-, Na+, CO2, Ca+).
- d. Imaging will be evaluated at screening and for clinical benefit every 12 weeks (3 cycles) of treatment, beginning at start of concomitant drug dosing (day 29 for phase I, day 1 for phase II).
- e. Isolated new lesions on bone scan at the first 12-week scan will be confirmed with a repeat bone scan at 6 weeks to rule out bone scan flair.
- f. Obtain if clinically warranted.
- g. +/- 3 days.
- h. PK assessments per Section 7.2.1(day 29, 43, 57 then monthly)
- i. Whole blood for CTC assessment will be collected on Day 1 of study drug administration.
- j. End of study visit – within 30 days of the last enzalutamide dose. Tumor assessment not necessary if done within preceding 30 days.
- k. Serum TSH and AM cortisol will be measured at day 1, 29, 57

1. EKG to assess QTcon study will be obtained Day 57 for Phase I, Day 29 for Phase II
- m. In calculating days of tests and measurements, the day a test or measurement is done is considered day 0. Therefore, if a test is done on a Monday, the Monday 4 weeks later would be considered day 28. Eligible patients will be seen in the outpatient clinic within two weeks of starting the study to have history and physical examination, ECOG performance status, concomitant medications, and baseline toxicity documented. To confirm eligibility, the patient will have standard of care screening labs drawn within four weeks of initiating therapy.

